20.2 APPENDIX II – Declaration of Helsinki

WORLD MEDICAL ASSOCIATION DECLARATION OF HELSINKI

Ethical Principles for Medical Research Involving Human Subjects

Adopted by the 18th WMA General Assembly

Helsinki, Finland, June 1964

And amended by the:

29th WMA General Assembly, Tokyo, Japan, October 1975

35th WMA General Assembly, Venice, Italy, October 1983

41st WMA General Assembly, Hong Kong, September 1989

48th WMA General Assembly, Somerset West, Republic of South Africa, October 1996

And the:

52nd WMA General Assembly, Edinburgh, Scotland, October 2000

A. INTRODUCTION

The World Medical Association has developed the Declaration of Helsinki as a statement of ethical principles to provide guidance to physicians and other participants in medical research involving human subjects. Medical research involving human subjects includes research on identifiable human material or identifiable data.

It is the duty of the physician to promote and safeguard the health of the people. The physician's knowledge and conscience are dedicated to the fulfillment of this duty.

The Declaration of Geneva of the World Medical Association binds the physician with the words, "The health of my subject will be my first consideration," and the International Code of Medical Ethics declares that, "A physician shall act only in the subject's interest when providing medical care which might have the effect of weakening the physical and mental condition of the subject."

Medical progress is based on research, which ultimately must rest in part on experimentation involving human subjects.

In medical research on human subjects, considerations related to the well being of the human subject should take precedence over the interests of science and society.

The primary purpose of medical research involving human subjects is to improve prophylactic, diagnostic and therapeutic procedures and the understanding of the etiology and pathogenesis of disease. Even the best-proven prophylactic, diagnostic, and therapeutic methods must continuously be challenged through research for their effectiveness, efficiency, accessibility and quality.

In current medical practice and in medical research, most prophylactic, diagnostic and therapeutic procedures involve risks and burdens.

Medical research is subject to ethical standards that promote respect for all human beings and protect their health and rights. Some research populations are vulnerable and need special protection. The particular needs of the economically and medically disadvantaged must be recognized. Special attention is also required for those who cannot give or refuse consent for themselves, for those who may be subject to giving consent under duress, for those who will not benefit personally from the research and for those for whom the research is combined with care.

Research Investigators should be aware of the ethical, legal and regulatory requirements for research on human subjects in their own countries as well as applicable international requirements. No national ethical, legal or regulatory requirement should be allowed to reduce or eliminate any of the protections for human subjects set forth in this Declaration.

B. BASIC PRINCIPLES FOR ALL MEDICAL RESEARCH

It is the duty of the physician in medical research to protect the life, health, privacy, and dignity of the human subject.

Medical research involving human subjects must conform to generally accepted scientific principles, be based on a thorough knowledge of the scientific literature, other relevant sources of information, and on adequate laboratory and, where appropriate, animal experimentation.

Appropriate caution must be exercised in the conduct of research, which may affect the environment, and the welfare of animals used for research must be respected.

The design and performance of each experimental procedure involving human subjects should be clearly formulated in an experimental protocol. This protocol should be submitted for consideration, comment, guidance, and where appropriate, approval to a specially appointed ethical review committee, which must be independent of the Investigator, the Sponsor or any other kind of undue influence. This independent committee should be in conformity with the laws and regulations of the country in which the research experiment is performed. The committee has the right to monitor ongoing trials. The researcher has the obligation to provide monitoring information to the committee, especially any SAEs. The researcher should also submit to the committee, for

review, information regarding funding, Sponsors, institutional affiliations, other potential conflicts of interest and incentives for subjects.

The research protocol should always contain a statement of the ethical considerations involved and should indicate that there is compliance with the principles enunciated in this Declaration.

Medical research involving human subjects should be conducted only by scientifically qualified persons and under the supervision of a clinically competent medical person. The responsibility for the human subject must always rest with a subject of the research, even though the subject has given consent.

Every medical research project involving human subjects should be preceded by careful assessment of predictable risks and burdens in comparison with foreseeable benefits to the subject or to others. This does not preclude the participation of healthy volunteers in medical research. The design of all studies should be publicly available.

Physicians should abstain from engaging in research projects involving human subjects unless they are confident that the risks involved have been adequately assessed and can be satisfactorily managed. Physicians should cease any investigation if the risks are found to outweigh the potential benefits or if there is conclusive proof of positive and beneficial results.

Medical research involving human subjects should only be conducted if the importance of the objective outweighs the inherent risks and burdens to the subject. This is especially important when the human subjects are healthy volunteers.

Medical research is only justified if there is a reasonable likelihood that the populations in which the research is carried out stand to benefit from the results of the research.

The subjects must be volunteers and informed participants in the research project.

The right of research subjects to safeguard their integrity must always be respected. Every precaution should be taken to respect the privacy of the subject, the confidentiality of the subject's information and to minimize the impact of the study on the subject's physical and mental integrity and on the personality of the subject.

In any research on human beings, each potential subject must be adequately informed of the aims, methods, sources of funding, any possible conflicts of interest, institutional affiliations of the researcher, the anticipated benefits and potential risks of the study and the discomfort it may entail. The subject should be informed of the right to abstain from participation in the study or to withdraw consent to participate at any time without reprisal. After ensuring that the subject has understood the information, the physician should then obtain the subject's freely-given informed consent, preferably in writing. If the consent cannot be obtained in writing, the non-written consent must be formally documented and witnessed.

When obtaining informed consent for the research project the physician should be particularly cautious if the subject is in a dependent relationship with the physician or may consent under duress. In that case the informed consent should be obtained by a well-informed physician who is not engaged in the investigation and who is completely independent of this relationship.

For a research subject who is legally incompetent, physically or mentally incapable of giving consent or is a legally incompetent minor, the Investigator must obtain informed consent from the legally authorized representative in accordance with applicable law. These groups should not be included in research unless the research is necessary to promote the health of the population represented and this research cannot instead be performed on legally competent persons.

When a subject deemed legally incompetent, such as a minor child, is able to give assent to decisions about participation in research, the Investigator must obtain that assent in addition to the consent of the legally authorized representative.

Research on individuals from whom it is not possible to obtain consent, including proxy or advance consent, should be done only if the physical/mental condition that prevents obtaining informed consent is a necessary characteristic of the research population. The specific reasons for involving research subjects with a condition that renders them unable to give informed consent should be stated in the experimental protocol for consideration and approval of the review committee. The protocol should state that consent to remain in the research should be obtained as soon as possible from the individual or a legally authorized surrogate.

Both authors and publishers have ethical obligations. In publication of the results of research, the Investigators are obliged to preserve the accuracy of the results. Negative as well as positive results should be published or otherwise publicly available. Sources of funding, institutional affiliations and any possible conflicts of interest should be declared in the publication. Reports of experimentation not in accordance with the principles laid down in this Declaration should not be accepted for publication.

C. ADDITIONAL PRINCIPLES FOR MEDICAL RESEARCH COMBINED WITH MEDICAL CARE

The physician may combine medical research with medical care, only to the extent that the research is justified by its potential prophylactic, diagnostic or therapeutic value. When medical research is combined with medical care, additional standards apply to protect the subjects who are research subjects.

The benefits, risks, burdens and effectiveness of a new method should be tested against those of the best current prophylactic, diagnostic, and therapeutic methods. This does not exclude the use of placebo, or no treatment, in studies where no proven prophylactic, diagnostic or therapeutic method exists.

At the conclusion of the study, every subject entered into the study should be assured of access to the best-proven prophylactic, diagnostic and therapeutic methods identified by the study.

The physician should fully inform the subject which aspects of the care are related to the research. The refusal of a subject to participate in a study must never interfere with the subject-physician relationship.

In the treatment of a subject, where proven prophylactic, diagnostic and therapeutic methods do not exist or have been ineffective, the physician, with informed consent from the subject, must be free to use unproven or new prophylactic, diagnostic and therapeutic measures, if in the physician's judgment it offers hope of saving life, re-establishing health or alleviating suffering. Where possible, these measures should be made the object of research, designed to evaluate their safety and efficacy. In all cases, new information should be recorded and, where appropriate, published. The other relevant guidelines of this Declaration should be followed.

20.5 APPENDIX V - Masking of the Treated Eye and Performance of the Primary Analysis

The following measures will be applied to keep the integrity of the database:

- The first masked review of data will be performed as late as possible, once all SAS programs are validated for study GS-LHON-CLIN-03B.
- Data will be cleaned and frozen up to and including the Week 48 visit.
- The cut-off date for the cleaning of subject visits will be recorded.
- A snapshot of the cleaned data base will be kept for statistical purposes and for possible inspection. The date of the snapshot will be recorded.
- A procedure will be written to trace data modification after the freeze of the database. Modifications will be listed in an appendix.
- The listing per subject of frozen visits (at least up to Week 48) will be provided and the status "ongoing" will be provided for unfrozen visits.
- A table will indicate the number of subjects with frozen data at each visit (for example 36/36 subjects at Week 48, 28/36 subjects at Week 72 and 23/36 subjects at Week 96).
- The masked team in charge of the collection and verification of data will remain masked up until the last visit (Week 96) of the last subject.
- For International coordinating investigators who review the Week 48 study report all efforts will be made to maintain their making regarding the individual subject results.
- Statistical results will be disclosed as late as possible. Date of disclosure will be recorded and a second snapshot of the data base will be done at that time.
- Review of listings of individual data will be restricted to very few people (e.g. for pharmacovigilance for safety data).
- The final masked review (Week 96) will exclude people who had access to unmasked individual subject data.
- No amendment of the SAP will be possible after the break of the randomization code. Any addition will be considered *a posteriori/ad-hoc* analyses.

11. **What is the primary purpose of the *Journal of Clinical Endocrinology and Metabolism*?**

11

11. **What is the primary purpose of the *Journal of Clinical Endocrinology and Metabolism*?**

—  
—

P

## 2. STUDY OBJECTIVES

### **Primary Objective:**

- To evaluate the efficacy of GS010 compared with sham at Week 48 in the change from baseline of the Log of the Minimal Angle of Resolution (LogMAR) in subjects affected for more than 6 months and up to 12 months by LHON.

## Secondary Objectives:

- To assess the effect of GS010 on parameters measured with high resolution spectral-domain optical coherence tomography (SD-OCT), including Retinal Ganglion Cell (RGC) layer, inner and outer nuclear layer (INL and ONL) thickness/volume, Retinal Nerve Fiber Layer (RNFL) thickness and topographical map analysis of these anatatomical regions.

- To evaluate the efficacy of GS010 compared with sham on the visual acuity (LogMAR) in a dynamic perspective through the comparison of the time course of the response.
- To verify whether the efficacy at Week 48 and at Week 96 of GS010 compared with sham and measured by the change from baseline of the LogMAR is dependent upon the treatment of the best- or worst-seeing-eye.
- To verify whether the rate of responders at Week 48 and 96 is dependent upon the treatment received and whether the magnitude of the treatment effect is dependent upon the treatment of the best- or worst-seeing eye at entry.
- To assess the effect of GS010 on standardized automated visual fields obtained with the Humphrey Visual Field (HVF) Analyzer II.
- To assess the effect of GS010 on contrast sensitivity measured with the Pelli-Robson chart.
- To assess the effect of GS010 on color vision measured with the Farnsworth-Munsell 100 Hue color test.

### 3. STUDY DESIGN

#### 3.1 OVERALL DESIGN

[figure not shown]
GS-LHON-CLIN-03B is a Phase III double-masked, sham-controlled, multicenter, multi-country study. Recruitment is competitive.

Both eyes will receive standard antiseptic preparation, administration of topical local ocular anesthetic agents and will undergo pupillary dilation. Administration of an intra-ocular pressure lowering agent will precede treatment. GS010 will be administered once during the study via a single intravitreal (IVT) injection. Sham IVT injection will be performed by applying pressure to the eye at the location of a typical procedure using the blunt end of a syringe without a needle.

The right eye of each subject will be randomly allocated to receive either GS010 or sham treatment in a 1:1 allocation ratio. The fellow (left) eye will receive the treatment not allocated to

the right eye. Therefore, each subject will receive GS010 in one eye and sham treatment in the fellow eye.

The schematic design of the study design is given below:

An algorithm with a testing hierarchy will be employed to determine the best- and worst-seeing eye of each subject prior to randomization. The randomization will be based on the right and left eye, because if the right eye is treated the left eye will receive sham and vice versa the treatment groups will be automatically balanced. However, the best- or worst-seeing eye at entry can be a confounding factor, and it cannot be discarded that the treatment effect will be the same in the best and worst seeing-eye. Secondarily, in order to verify this hypothesis with optimal power, an adaptive randomization technique called Efron's minimization ([Efron 1971](#)) method will be used to minimize the imbalance of treatment groups between the best-seeing eyes and worst-seeing eyes.

Masking will be accomplished with sham injection of the fellow eye. Thus treatment allocation will be double-masked for both the subject and the investigation (follow-up) team, except the physician and medical team that will perform the GS010 administration and sham injection and the first follow-up visit. Centralized analysis of the Early Treatment Diabetic Retinopathy Study (ETDRS) visual acuity results, automated visual fields, SD-OCT, color vision and contrast sensitivity will be performed.

### 3.2 DURATION AND SCHEDULE OF STUDY PARTICIPATION

#### Study Schedule

The trial is divided into the following visits:

---

Screening Visit (Visit 1): From 28 to 2 days before the investigational medicinal product (IMP) administration. This visit will allow Investigators to assess subject eligibility based on selection and non-selection criteria.

Inclusion Visit (Visit 2): 1 day before the IMP administration. This visit will allow Investigators to confirm the subject's eligibility based on inclusion and exclusion criteria. Subjects will undergo baseline ophthalmological testing.

After the subject is confirmed to be eligible for the study, the right eye will be randomized to GS010 or sham treatment based on a predefined central randomization scheme.

Treatment Visit (Visit 3): Day of the IMP administration. Subjects will receive GS010 by IVT injection according to the randomized treatment assigned. The fellow eye will receive the alternative treatment.

Follow-up visits (Visits 4 to 12): Nine follow-up visits after the IVT procedure will be conducted at 24 hours and 2, 4, 8, 12, 24, 48, 72, and 96 weeks.

The study plan is shown in Section 4.2 of V3.0 of the protocol.

Study duration:

Initiation of the trial with the first subject's first visit is planned for late Q4 2015. The estimated recruitment period is 12 months and will be dependent on recruitment rate. Total study follow-up is 96 weeks and the study will end with the last subject's last visit. The last subject's last visit is estimated to occur late Q4 2018. Therefore, the estimated study duration is 3 years.

At the end of this initial study period, a long-term safety and efficacy study as detailed in a future separate protocol will be initiated for further evaluation of the safety and efficacy durability. The long term safety study duration will be conducted according to current regulatory authority recommendation.

### 3.3 SAMPLE SIZE CONSIDERATIONS

Sample size calculation is based on the primary endpoint (LogMAR) and on the paired comparison of treated and sham eye. There is no published data regarding the within subject variance and the sample size calculation through paired comparison will therefore be very speculative for two reasons. The first reason is the within subject correlation between right and left eye and the second reason is the absence of information on the within and between subject variance of the LogMAR. Usually the within subject correlation is positive and the use of a null correlation is conservative. The absence of information on the LogMAR requires a second rough approximation of the mean and variance of LogMAR because the mean of ETDRS (Lam et al. 2014) is highly correlated to the variance of ETDRS ( $R^2 = 0.839$  for the log-log relationship). This correlation is in favor of the use of the LogMAR to stabilize the variance but the transformation from ETDRS mean and variance to LogMAR mean and variance requires additional assumptions. Starting with a mean 23.4 and a standard deviation of 28.3 (Lam et al.

2014) and a difference of 20 letters on average between treated and sham eye, using the relationship between the log mean and the log variance obtained with Lam et al. (2014) results (log variance = 1.743 log mean + 0.48,  $R^2 = 0.839$ ) and assuming a perfect lognormal distribution of ETDRS, the difference in means of the lognormal distributions is 0.65 (3.32 - 2.67) and the pooled standard deviation of the log distributions is 0.914. Assuming no correlation between both eyes, the within subject standard deviation is  $(2 \times 0.914^2)^{0.5} = 1.29$ . The standardized difference in means is therefore  $0.65/1.29 = 0.504$  rounded to 0.50. The sample size required to get a power of 85% is exactly 36 subjects.

In GS-LHON-CLIN-01(Phase I/II study), at week 48 the standard deviation (SD) for visual acuity of the between-eye difference in change from baseline was calculated as 0.594. Considering that in Phase III studies of GS010 detection of a 15 ETDRS letters or 0.3 LogMAR difference between treated and untreated eyes at outcome is a clinically reliable difference, the SD of the difference of 0.594 would provide a power/probability of 84% to detect such a difference based on the enrolment goal of 36 subjects each in the RESCUE and REVERSE Phase III clinical trials.

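### The stated 85% power with exactly 36 subjects is a normal-approximation figure; a paired t calculation gives 83%, and the log-scale inputs cannot be traced to the stated starting values (minor)

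*SAP*

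**What the plan says.** SAP 3.3 and protocol 12.2 carry the same derivation. It begins from published ETDRS data ("Starting with a mean 23.4 and a standard deviation of 28.3"), posits a 20-letter advantage for the treated eye, applies a log-log relation between variance and mean (slope 1.743, intercept 0.48, base of the logarithm not given), and assumes that ETDRS scores are lognormal. From this it reports that "the difference in means of the lognormal distributions is 0.65 (3.32 - 2.67) and the pooled standard deviation of the log distributions is 0.914". With zero correlation between eyes, the SD of the paired difference is (2 × 0.914²)^0.5 = 1.29 and the standardized difference is 0.65/1.29 = 0.504, which is then rounded to 0.50. The conclusion drawn is: "The sample size required to get a power of 85% is exactly 36 subjects".

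The SAP alone adds a second calculation based on the Phase I/II study. For a 0.3 LogMAR difference and 36 subjects, "the SD of the difference of 0.594 would provide a power/probability of 84% to detect such a difference".

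Neither calculation names the test or formula behind its power figure.

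**The concern.** At a fixed sample size and alpha, power rises with the standardized effect. Yet the SAP gives 85% at 0.50 and 84% at 0.505, both with 36 subjects. One method cannot produce both figures. The claim that 36 is exact also suggests a precision that depends on treating the SD of the difference as known, whereas the trial will estimate it from 36 pairs.

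A second difficulty lies upstream. The log means and SD that lead to 0.504 are presented as following from 23.4 letters, a 20-letter difference and the variance relation. If they do not, the effect size cannot be verified from the text.

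This derivation is the only sample-size justification in the protocol and the first of two in the SAP. At stake are the accuracy and traceability of the power quoted for a pivotal trial.

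**Working it through.** **Inputs.** From SAP 3.3: d = 0.50 (0.504 unrounded), n = 36, log means 2.67 and 3.32, pooled log SD 0.914, starting mean 23.4 and SD 28.3 letters, difference 20 letters, and the variance relation. From the Phase I/II paragraph: 0.3 LogMAR and SD 0.594. Alpha of 0.05 and a two-sided alternative come from SAP 9.5.1 (primary analysis for EMA); the sample-size section does not restate them. I assume 36 complete pairs, a sham mean of 23.4 and a treated mean of 43.4.

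**1. Reproducing the stated figure.** Normal approximation: n = (1.960 + 1.036)² / 0.50² = 35.9, so 36. Power at 36 = Φ(0.50 × √36 − 1.960) = Φ(1.04) = 85.1%. This is the plan's figure.

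**2. Estimated SD.** Noncentral t with n − 1 df and noncentrality d√n (3.0 at d = 0.50, n = 36):

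| n | d = 0.50 | d = 0.504 |
|---|---|---|
| 36 | 83.1% | 83.6% |
| 37 | 84.1% | 84.7% |
| 38 | 85.1% | 85.7% |

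On this basis 85% needs 38 subjects at either value of d.

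**3. The two SAP powers side by side, n = 36.**

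| Calculation | d | Normal | Paired t | Stated |
|---|---|---|---|---|
| Published data | 0.50 | 85.1% | 83.1% | 85% |
| Phase I/II | 0.3/0.594 = 0.505 | 85.8% | 83.8% | 84% |

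The first stated figure matches the normal column and the second matches the t column.

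**4. Log-scale inputs.** For a lognormal, arithmetic mean = exp(log mean + s²/2) and s² = ln(1 + variance/mean²).

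- *Do 2.67, 3.32 and 0.914 agree with each other?* Yes. exp(2.67 + 0.914²/2) = 21.9 and exp(3.32 + 0.914²/2) = 42.0 letters, a difference of 20.1.
- *Do they agree with 23.4?* No. A mean of 23.4 with log mean 2.67 needs s = √[2(ln 23.4 − 2.67)] = 0.983. A mean of 43.4 with log mean 3.32 needs s = 0.949. Both exceed 0.914.
- *Does the stated relation return them?* No. At 23.4 and 43.4, base 10 gives log means 2.73 and 3.39 with pooled SD 0.899. Natural logarithms give 2.88 and 3.53 with pooled SD 0.714.

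The effect on power depends on which figures are kept (d = difference/(SD × √2), paired t, n = 36):

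| Reconciliation | Log difference | Pooled SD | d | Power |
|---|---|---|---|---|
| Keep 2.67 and 3.32, use implied SDs | 0.65 | 0.966 | 0.476 | 79.3% |
| Keep SD 0.914 for both eyes | 0.618 | 0.914 | 0.478 | 79.6% |
| SD 28.3 for sham, treated variance scaled by slope 1.743 | 0.663 | 0.925 | 0.507 | 84.1% |
| Relation in base 10 for both eyes | 0.662 | 0.899 | 0.521 | 85.9% |
| SD 28.3 for sham, base-10 relation for treated | 0.687 | 0.912 | 0.532 | 87.4% |

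The natural-log version gives d = 0.643 and 96% power, but it implies an SD of 19.8 letters at a mean of 23.4, against the stated 28.3. Base 10 implies 27.1 and is the likelier reading, so I leave the natural-log result out of the range.

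**The case against.** The strongest reply is that this lies within ordinary tolerance. Normal and t calculations differ here by about 2 points of power and 2 subjects, and the stated figure does reproduce under a standard formula. Like for like, with the unrounded 0.504, the t method gives 83.6% and 83.8% for the two calculations, which are practically equal. Both documents describe the derivation as highly tentative and call zero between-eye correlation conservative. As an illustration with an assumed value, a correlation of 0.05 at SD 0.914 raises d to 0.516 and t power to 85.3%. The SAP also supports 36 subjects separately through the Phase I/II data. All of this stands and is why the point is minor. It does not rescue the word exactly, or two adjacent powers that move the wrong way.

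Three stronger readings are tempting and are not supported:

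- *That the SAP declares a paired t-test for its 84%.* It names no test there. The t method is inferred from the fit after rounding (83.8% against 85.8%).
- *That the log means and SD contradict each other.* They do not: together they give a 20.1-letter difference. The mismatch is with the starting mean of 23.4 and the variance relation.
- *That true power is 79%.* This keeps the log means, or the SD, and ignores the variance relation. The three reconciliations that use the stated SD of 28.3 or the base-10 relation all give d above 0.50, and two of them support 85% at 36 even with the t-test.

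**Conclusion.** Wrong as written, but minor. The 85% for 36 subjects is a normal-approximation figure at d = 0.50. Allowing for an estimated SD, power is 83% and 85% needs 38 subjects. The SAP's 85% and 84% were not computed by one method. The values 2.67, 3.32 and 0.914 do not follow from the stated starting mean and variance relation. That is a traceability defect of undetermined direction, spanning about 79% to 87% t power at 36.

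The 83% assumes two-sided alpha 0.05, 36 complete pairs and a paired t as a stand-in for the planned mixed-model ANCOVA, whose baseline adjustment is not modelled here. The 79% to 87% range also assumes that 23.4 letters is the sham mean. Nothing here shows that 36 subjects are too few, and no hypothesis, analysis or decision rule is affected.

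**What to change.** In SAP 3.3 and protocol 12.2, replace the power sentence with: *36 subjects give 83% power (paired t-test, two-sided alpha 0.05, standardized difference 0.50).* Rederive the log means and pooled SD from the stated inputs, give the base of the logarithm, and restate the standardized difference and power if they change.

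Alternatively, rest the sample size on the Phase I/II-based statement (0.3 LogMAR, SD 0.594, 36 subjects, 84%), which reproduces under a paired t. Name the test there and add the statement to protocol 12.2, which does not contain it.

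Either route is a text edit. With the first, the quoted power falls by about 2 points before any rederivation; the sample size is unchanged. Protocol Appendix V bars SAP amendments once the randomization code is broken, so the SAP edit belongs before that.
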